**MRI and Biological Markers of Acute E-Cigarette Exposure in Smokers and Vapers**

**NCT 03479203**

**September 15, 2017**

[figure not shown]
To determine the acute effects of e-cig aerosol inhalation we will quantify surrogate markers of EDF at the micro- and macro-vascular level before and after a nicotine-free e-cig aerosol in healthy subjects without history of cardiovascular disease.

In order to isolate and assess the acute effects of inhaled aerosol on surrogate MRI markers of EDF (endothelial dysfunction), nicotine-naïve (i.e. non-smokers) will undergo an e-cig aerosol inhalation challenge using a commercially available, disposable, non-flavored nicotine-free e-cig (ECO series, epuffer.com).

All MR procedures will be performed on a 3T Siemens TIM Trio imager (Siemens Medical Solutions) using standard RF coils (8-channel extremity coil for cuff paradigm studies at the location of the femoro-popliteal artery and vein, and a combination of two body matrix and 12-channel head coils for PWV (pulse wave velocity) of the aorta and neurovascular reactivity in the superior sagittal sinus (SSS) in conjunction with the custom-designed pulse sequences. Subjects will be asked to fast for eight hours, have abstained from taking vasoactive medications (including over-the-counter medications) as well as vigorous physical activity. Each visit will comprise two blood draws and two qMRI (quantitative magnetic resonance imaging) examinations, one before and one after an e-cig challenge to assess the changes in the functional and mechanical metrics described in the previous section. The e-cig challenge will consist of 16 two-second-long puffs (equivalent to smoking one conventional cigarette). Smoking will be directly supervised to prevent superficial smoking or hyperventilation by the study subjects. The challenge will last approximately 20 minutes. A second blood draw will be taken six hours after the e-cig challenge. From the blood samples collected, inflammatory biomarkers will be assessed.

Blood will be drawn from the antecubital vein of the subject's left or right arm. At least 2 mL of plasma will be isolated and kept frozen after centrifuging blood for 15 min.

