### Analyses

Descriptive statistics will initially be performed to determine the characteristics of the various distributions and to identify outliers by displaying the data in the form of box and whisker plots and by computing means and standard deviations. Acute changes from baseline (blood draws pre- and post e-cig aerosol challenge) will be evaluated by paired t-tests for each of the variables listed above. To compare the qMRI metrics with inflammatory indices, Spearman correlations will be performed. We expect moderate inter-modality correlations ( $R^2 \sim 0.5$ ) for individual qMRI measures. We then use linear regression to create a classification model using the eight qMRI indices jointly. We expect  $R^2 > 80\%$ , substantially greater than each individual parameter alone, indicating that inhaled e-cig aerosol promotes *systemic EDF*.

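### The eight-index regression has no named outcome or classes, and its expected R² above 80% cannot show that the aerosol promotes systemic endothelial dysfunction

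*Combined protocol and SAP*

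**What the plan says.** The opening description sets out one group, nicotine-naïve non-smokers, who "will undergo an e-cig aerosol inhalation challenge using a commercially available, disposable, non-flavored nicotine-free e-cig". Each visit has "two qMRI (quantitative magnetic resonance imaging) examinations, one before and one after an e-cig challenge", with paired blood draws. No comparison group is described in the body, although the title refers to smokers and vapers.

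Data and Statistical Analysis specifies two-tailed paired t-tests at 0.05 for each qMRI parameter, and a multivariate regression on within-subject changes. The Analyses section adds paired t-tests for the blood markers and then proceeds in this order:

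- "To compare the qMRI metrics with inflammatory indices, Spearman correlations will be performed".
- "We expect moderate inter-modality correlations", with R² of about 0.5 for individual qMRI measures.
- "We then use linear regression to create a classification model using the eight qMRI indices jointly".
- An expected R² above 80%, "substantially greater than each individual parameter alone, indicating that inhaled e-cig aerosol promotes" systemic endothelial dysfunction.

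No dependent variable, classes, handling of the repeated scans, validation or sample size is given for the joint model.

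**The concern.** This is the only analysis from which the plan draws a conclusion about a systemic effect. A classification model needs classes and a regression needs an outcome, and the text supplies neither. The question is whether any reasonable way of filling the gap makes a high R² evidence that the aerosol changed vascular function.

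If none does, the study could report a systemic effect on the strength of an overfitted association. It could equally report a low R² and appear to contradict a real, consistent change. The two errors run in opposite directions, and which one applies depends on an outcome that has not been named.

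**Working it through.** **Inputs.** From the documents: eight predictors, single-index R² about 0.5, joint R² above 0.80, one group scanned before and after. Assumed, because the documents give none: sample size n, standardized paired effect dz (mean change divided by SD of change), pre/post correlation ρ, and correlation between indices.

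**Step 1. Can the plan's own figures be consistent?** For eight equally correlated predictors (mutual correlation c), each with r² = 0.5 against a common outcome, R² = 8 × 0.5/(1 + 7c).
- R² = 0.80 gives 1 + 7c = 5, so c = 0.57.
- R² = 1.0 gives c = 0.43.

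The step from 0.5 to above 0.8 is therefore possible, for c between 0.43 and 0.57, when the outcome is the same in both. This supports reading the outcome as an inflammatory index.

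**Step 2. Reading A: the outcome is an inflammatory index, one row per subject.** R² from a regression with an intercept is unchanged if a constant is added to every subject's value of any variable. The mean pre-to-post change, which is the aerosol effect, is such a constant. R² can thus be high with no mean change, or low with a large one.

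Chance also matters. With no association and normal errors, R² follows Beta(4, (n−9)/2), with mean 8/(n−1).

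| n (assumed) | Mean R² under no association | P(R² > 0.8) |
|---|---|---|
| 10 | 0.89 | 0.80 |
| 11 | 0.80 | 0.59 (= 1 − 0.8⁴) |
| 12 | 0.73 | 0.40 |
| 15 | 0.57 | 0.10 |
| 20 | 0.42 | 0.006 |
| 30 | 0.28 | below 0.001 |

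**Step 3. Reading B: the outcome is the pre/post label, scans treated as independent.** For two equal classes R² = D²/(D² + 4), where D is the multivariate separation in SD units. R² = 0.80 gives D² = 16 and D = 4, with Φ(2) = 97.7% of scans correctly labelled.

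For one index D = dz√(2(1−ρ)), so D = 4 requires dz = 2.83, 4.0, 6.3 or 8.9 at ρ = 0, 0.5, 0.8 or 0.9.

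Take eight indices, each with dz = 1 and ρ = 0.8, so each contributes 0.4 to D² before allowing for inter-index correlation:
- Independent indices: D² = 8 × 0.4 = 3.2, and R² = 3.2/7.2 = 0.44.
- Inter-index correlation 0.5: D² = 3.2/(1 + 7 × 0.5) = 0.711, and R² = 0.711/4.711 = 0.15.

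By simulation at n=20, fitted R² exceeds 0.8 with probability 0.005 or less in both cases. Power is 98.9% for the paired t-test on one index, and about 100% and 91% respectively for a paired Hotelling T².

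There are exceptions. At n=10, dz = 1, ρ = 0.5 and independent indices, R² exceeds 0.8 in about 64% of trials.

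**Step 4. What the rest of the plan would detect, and what could replace the joint model.** Simulated power at n=20, ρ = 0.8, inter-index correlation 0.5, with a shift of 0.5 between-subject SD in the affected indices:

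| Indices that change | Bonferroni paired t-tests (at least one) | Paired Hotelling T² | t-test on average standardized change |
|---|---|---|---|
| All eight | 97% | 71% | 99% |
| Two | 84% | 94% | 20% |
| One | 69% | 71% | 9% |

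The T² figure is the same in the first and last rows because D² is equal: 8 × 0.25/4.5 = 0.444 for eight indices, and 0.25 × 2 × (1 − 0.5/4.5) = 0.444 for one. In the all-eight case, an unpaired regression on the pre/post label has mean fitted R² of 0.19, and its F-test is significant in about 2% of trials.

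**The case against.** The strongest defence is that classification is simply the wrong word. The joint model follows the Spearman comparison, and 0.8 can be set against 0.5 only if both refer to the same outcome, so the authors probably meant to predict an inflammatory index. On that reading the model need not involve the pre/post label at all, and the regression on within-subject changes shows that the authors know how to keep the pairing. This stands. A reader might infer that the plan classifies pre against post scans and discards the pairing; the text does not say so, and the 4-SD result is conditional on that reading.

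A reader might also take 80% as a pass mark that the trial must reach. The plan words it as an expectation with an interpretation attached, not as a decision threshold.

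Nor would the plan as a whole miss a real effect. The per-index paired t-tests detect at least one change in 97% of simulated trials when all eight indices shift, even after a Bonferroni correction.

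Finally, the title's reference to smokers and vapers might suggest that the classes are groups of people. The body describes no such groups. If it did, separating them would show a group difference and would still not establish an aerosol effect.

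None of this rescues the inference. Under the reading most favourable to the authors, R² still describes association across subjects and not change after exposure.

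**Conclusion.** The point holds in a limited form and should be corrected before analysis. The outcome and classes of the joint model are undefined, and concluding systemic dysfunction from a high R² is unsound under both readings. Under the inflammatory-index reading that is exact algebra for one row per subject, and overfitting adds to it: R² above 0.8 arises by chance with probability 0.80 at n=10, falling to 0.006 at n=20. Under the pre/post reading, R² of 0.80 demands a 4-SD separation, which strong paired effects usually fall short of.

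The chance probabilities depend on n, and the power figures on n, effect size and correlations; the documents state none of these. At n of 20 or more, chance alone is no longer a serious explanation for R² above 0.8, but the mismatch between R² and the aerosol effect remains at any n. The documents do not support saying that the trial has no valid test of change, because the single-index tests are sound for that purpose. What lacks support is the joint, systemic claim.

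**What to change.** 1. Remove the statement that R² above 80% indicates systemic endothelial dysfunction.
2. Base the joint conclusion on a paired analysis of the eight within-subject changes, chosen and written down in advance: multiplicity-adjusted paired t-tests, or a paired Hotelling T² (which needs n above 8 and is weak close to that limit; about 44% power in the n=10 exception above). Use an average of standardized changes only if a common shift across indices is the stated hypothesis, with the adverse direction of each index fixed beforehand.
3. List the eight indices and name the outcome of the regression. Keep the regression of inflammatory change on qMRI changes as exploratory prediction, report adjusted or cross-validated R² alongside n, and do not call it a classification model.

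The cost is a paragraph of SAP text and slightly more analysis on data already being collected. The joint test must be fixed in advance, and the reported R² will look less favourable. The averaged test carries a real risk, with about 9% power if one index changes and 20% if two do. That matters because the plan itself asks which metric is most sensitive, and so allows for unequal responses.

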### Data and Statistical Analysis

The fractional changes in functional and mechanical qMRI parameters between pre- and post-nicotine challenge will be determined. For each parameter paired two-tailed t-tests will be performed with  $p < 0.05$  indicating statistical significance. The data will allow us to determine which of the qMRI metrics (peripheral vascular reactivity, central arterial stiffness or neurovascular reactivity), are most sensitive to e-cig aerosol inhalation. We will also further conduct multivariate regression analysis on the within-subject changes controlling for other subject-specific covariates.

To quantify the changes in the levels of inflammatory biomarkers in serum collected from study participants before and after e-cigarette aerosol exposure and compare these metrics with qMRI-derived biomarkers.

Blood drawn from the antecubital vein by a phlebotomist from study participants will be collected into tubes containing clot activator. Serum will be separated within 30 minutes by centrifugation and stored at  $-70^{\circ}\text{C}$  prior to analysis. Inflammatory biomarkers will be detected via enzyme-linked immunosorbent assay (ELISA) techniques from blood draws #1 and 2. MCP-1 and MIP-1 concentrations will be measured using commercially available ELISA kits (R&D Systems, Abingdon, UK); sICAM, sRAGE, IFN- $\gamma$  and TNF- $\alpha$  with RayBiotech kits

(RayBiotech, Inc., Norcross, GA 30092); HMGB1 will be assayed by ELISA kits supplied by IBL International (IBL GmbH).

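### The systemic-EDF conclusion is attached to a joint R², which carries no direction, and not to the signed pre-to-post changes that the plan already tests

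*Combined protocol and SAP*

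**What the plan says.** The plan has three relevant strands.

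- **Signed changes in qMRI.** Data and Statistical Analysis computes fractional pre-to-post changes. It then states: "For each parameter paired two-tailed t-tests will be performed with" a 0.05 threshold. It adds: "We will also further conduct multivariate regression analysis on the within-subject changes controlling for other subject-specific covariates".
- **Signed changes in blood markers.** In Analyses, changes between the two blood draws "will be evaluated by paired t-tests for each of the variables listed above". Seven markers are named: MCP-1, MIP-1, sICAM, sRAGE, IFN-γ, TNF-α and HMGB1.
- **Association and the joint model.** Analyses continues: "To compare the qMRI metrics with inflammatory indices, Spearman correlations will be performed". "We expect moderate inter-modality correlations", with R² near 0.5 for individual qMRI measures. Then: "We then use linear regression to create a classification model using the eight qMRI indices jointly". The expected joint R² is above 80%, "substantially greater than each individual parameter alone, indicating that inhaled e-cig aerosol promotes" systemic EDF.

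The dependent variable of the joint regression is not stated. Nor is it stated whether the indices enter as levels or as changes. The opening section refers to metrics "to assess the changes in the functional and mechanical metrics described in the previous section". That earlier section is not in the available text and may list the eight indices and their adverse directions.

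**The concern.** To say that aerosol *promotes* dysfunction is a claim about the direction of a mean change. The sentence that makes this claim rests it on R², which measures how well one set of variables predicts another. The analyses that estimate direction sit elsewhere in the plan, and the sentence does not refer to them.

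The study's headline interpretation is at stake. A team following the text could obtain a high joint R² and report systemic EDF although the mean qMRI changes are nil or favourable.

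**Working it through.** **Inputs.** From Analyses: eight indices, single-index R² about 0.5, joint R² above 0.8. From Data and Statistical Analysis: two-tailed paired t-tests at 0.05. The sample size, the correlations among indices and the outcome are not given, so the 80% figure cannot be re-derived. Values of n and of the mutual correlation below are assumptions.

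**1. Outcome is a biomarker change (natural reading).** The model is yᵢ = a + Σⱼ bⱼxᵢⱼ + eᵢ, and R² = 1 − SSE/SST. Add any constant mⱼ to index j and m_y to the outcome. The slopes and residuals do not move; the intercept becomes a + m_y − Σ bⱼmⱼ. SSE and SST are unchanged, so R² is unchanged.

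Numerical check (simulated, n = 30):

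| Mean shift in all changes | R² | Mean paired t over the eight indices |
|---|---|---|
| −0.8 SD | 0.865 | −5.46 |
| 0 | 0.865 | −0.59 |
| +0.8 SD | 0.865 | +4.29 |

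**2. Outcome is pre/post status (suggested by the term classification).** Reversing the sign of every index reverses the slopes and leaves the fitted values alone. An adverse pattern and its exact mirror image therefore give the same R² (0.864 and 0.864 in a simulated n = 30 example). This holds even if some indices worsen by rising and others by falling. Here R² does show that the indices changed; it does not show which way.

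**3. Illustration under the plan's own expectation, biomarker reading.** Take eight equally correlated indices, each with R² 0.5 to the outcome and mutual correlation ρ:

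joint R² = 8 × 0.5 / (1 + 7ρ) = 4 / (1 + 7ρ).

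This is at most 1 if ρ ≥ 3/7 = 0.43, and exceeds 0.8 if ρ < 4/7 = 0.57. Two values in that range:

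- ρ = 0.50: 4/4.50 = 0.89
- ρ = 0.55: 4/4.85 = 0.82

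With every mean change set to zero (4,000 simulated studies per cell):

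| n (assumed) | R² > 0.8, ρ = 0.50 | and no qMRI paired test significant | R² > 0.8, ρ = 0.55 | and no qMRI paired test significant |
|---|---|---|---|---|
| 15 | 99.0% | 74.2% | 95.2% | 72.5% |
| 20 | 99.0% | 74.6% | 92.8% | 71.2% |
| 30 | 99.3% | 74.5% | 89.4% | 68.5% |
| 60 | 99.7% | 74.6% | 86.6% | 67.7% |

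**4. Which R² to report.** An in-sample joint linear R² can never be below any single-index linear R² on the same data, so part of the expected gain is automatic. At ρ = 0.55 (true value 0.82), mean values over 3,000 simulated studies per n were:

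| n (assumed) | In-sample | Adjusted | Leave-one-out |
|---|---|---|---|
| 15 | 0.915 | 0.802 | 0.32 |
| 20 | 0.889 | 0.808 | 0.60 |
| 30 | 0.866 | 0.814 | 0.72 |
| 60 | 0.844 | 0.819 | 0.78 |

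Adjusted and leave-one-out R² answer different questions and are far apart at small n, so the plan should name one.

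**5. Why a rule for *systemic* is needed.** In the same zero-change model, at least one of eight unadjusted 95% intervals excludes zero in about 25% of studies, and in a given direction in about 12% to 14%. Moving the claim to the paired changes without saying which pattern counts would leave it loose.

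**The case against.** The best defence is that the 80% is worded as an expectation, with no test or success criterion attached. The sentence can be read charitably: the paired tests establish whether function changed, and a joint model that beats each single index suggests that several vascular beds are involved, hence *systemic*. Context also points to an inflammatory marker as the outcome, because the regression follows directly from the comparison of qMRI with blood markers. The missing earlier section may define adverse directions. And the paired tests would expose a null or favourable result.

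Much of this stands. A reader might infer that R² above 80% is a formal decision rule; the text does not support that. A reader might also infer that the plan never examines direction; it does, through the paired tests. What remains is that the sentence states how a high R² will be interpreted and makes that interpretation conditional on nothing else. Naming the outcome would not give R² a sign, and the text would still not say which of seven biomarkers is meant.

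It is also fair to object that the percentages in step 3 are partly built in, since the true joint R² was set at 0.82 or 0.89. They illustrate the algebra if the plan's optimistic correlations are true, and nothing more.

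**Conclusion.** The concern holds as a flaw of inference in one clause. It should be corrected before results are interpreted. The core is exact and needs no assumption about n: R² is blind to direction on both readings of the outcome, and blind to the size of the mean change on the biomarker-change reading.

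Three stronger conclusions should not be drawn. First, R² is not uninformative about change on every reading: with pre/post status as outcome it does show that a change occurred. Second, the 87% to 99.7% range is not the probability of a false claim in this trial; it assumes the plan's expected correlations, equal mutual correlations and an n the plan does not state. Third, correcting the clause would not by itself justify *promotes*: the available text describes no control session, which is a separate limit on causal wording.

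**What to change.** Two changes, both needed.

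**(a) Move the conclusion.** Delete the clause from the word *indicating* onward. State that any systemic-EDF claim rests on the mean pre-to-post qMRI changes with 95% CIs. Fix the adverse direction of each metric in advance, citing the earlier section mentioned in the opening text if it already does so. Fix a rule in advance as well. One example is a significant adverse change in at least one metric of each of the three domains (peripheral, central, neurovascular), with multiplicity adjustment within a domain.

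**(b) Keep the joint regression as description.** Use one row per subject, with biomarker change regressed on the changes in the eight qMRI indices. Show it for all seven biomarkers. Report leave-one-out R² beside single-index linear R² computed the same way, and report the Spearman results separately, since they are a different measure.

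**Cost.** A few sentences of SAP wording and a few lines of code; no new data or visits. The reported joint R² will be lower: at ρ = 0.55, about 0.87 in-sample against 0.72 leave-one-out at an assumed n = 30, and about 0.91 against roughly 0.3 at n = 15. There will be seven results in place of one, and the word *systemic* will be harder to earn.

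### A joint R-squared above 80% cannot show that aerosol promotes systemic EDF; separately, the planned paired changes cannot be attributed to aerosol alone or used to name the most sensitive metric

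*Combined protocol and SAP*

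**What the plan says.** The opening study description sets out to isolate the acute effect of inhaled aerosol. Non-smokers inhale a nicotine-free aerosol, and "Each visit will comprise two blood draws and two qMRI (quantitative magnetic resonance imaging) examinations, one before and one after an e-cig challenge". For blood, "A second blood draw will be taken six hours after the e-cig challenge". No sham, air-only or no-aerosol session and no unexposed group is described.

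Under Data and Statistical Analysis, "The fractional changes in functional and mechanical qMRI parameters between pre- and post-nicotine challenge will be determined". Each parameter then gets a two-sided paired t-test at 0.05, followed by a regression of within-person changes on subject covariates. The section says the data will show which qMRI metrics "are most sensitive to e-cig aerosol inhalation".

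Under Analyses, qMRI metrics are correlated with inflammatory indices, with an R-squared of about 0.5 expected for individual measures. Then: "We then use linear regression to create a classification model using the eight qMRI indices jointly". The outcome of that regression is not named. The expected joint R-squared is above 80%, "substantially greater than each individual parameter alone, indicating that inhaled e-cig aerosol promotes" systemic EDF.

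**The concern.** The R-squared sentence fixes in advance how a result will be read, and the reading is causal and directional. R-squared says how well one variable is predicted from others. It does not say whether anything rose or fell after the challenge, or why. The trial could therefore report that aerosol promotes systemic EDF when no average changed.

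Two separate weaknesses affect the other headline statement. A paired change in a session that always contains aerosol estimates aerosol plus whatever else differs between the two measurements. And one test per metric, each against zero, does not show that one metric responds more than another.

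**Working it through.** **Inputs from the documents.** Eight indices; individual R-squared about 0.5; joint R-squared above 0.80; two-sided paired t-tests at 0.05. No sample size, SD, correlation between indices or drift is given. I assume n = 20 and n = 30 and express shifts in SDs of the paired change.

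**1. The plan's own figure.** With eight predictors, each with R-squared 0.5 and a common correlation ρ between them, joint R-squared = 8 × 0.5 / (1 + 7ρ). It stays at or below 1 only if ρ ≥ 3/7 = 0.43, and exceeds 0.80 only if ρ < 4/7 = 0.57. At ρ = 0.5 it is 4/4.5 = 0.89; at ρ = 0.6 it is 4/5.2 = 0.77. The expectation is possible but cannot be reproduced, because ρ is not given.

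**2. Outcome is a marker change.** R-squared = 1 − Σ(y − ŷ)² / Σ(y − ȳ)². Add a constant a to every y and b_j to every value of predictor j. The slopes stay the same, the intercept absorbs a − Σβ_j b_j, and ŷ and ȳ both rise by a. Neither sum changes, so R-squared does not change. The paired t statistic, mean / (SD/√n), does.

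Illustration: one common factor with loading 0.75 on each index change and 0.943 on the marker change.
- Individual R-squared: (0.75 × 0.943)² = 0.50.
- Correlation between indices: 0.75² = 0.5625. Joint R-squared: 4 / (1 + 7 × 0.5625) = 0.81.

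| Mean change in every variable | Quantity | n = 20 | n = 30 |
|---|---|---|---|
| 0 | R-squared > 0.80 | 89% | 86% |
| 0 | Paired t-test on one index, p < 0.05 | 5% | 5% |
| 0.5 SD | R-squared > 0.80 | 89% | 86% |
| 0.5 SD | Paired t-test on one index, p < 0.05 | 55% | 75% |

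Repeat runs gave 89–90% at n = 20 and 84–86% at n = 30 for R-squared. Within each simulated study, R-squared with and without the shift agreed to better than 1e-15.

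The invariance is for a constant shift in the changes as analysed. A constant shift in raw units is not constant in fractional changes and can move R-squared somewhat.

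A no-aerosol session does not help here. The same algebra holds if every variable is an aerosol-minus-control change.

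**3. Outcome is pre versus post.** R-squared then rises with the mean shift. But the model sees only the total, aerosol plus session, so any split of the same total gives the same R-squared.

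**4. Paired changes.** The expected change is aerosol effect + session effect. Everyone is exposed, so the two are never observed apart, and a covariate regression leaves any shift common to all subjects in its intercept. For qMRI the session effect includes repeat cuff and breath-hold testing and the puffing manoeuvre. For the six-hour draw it includes time of day and fed state; an eight-hour fast is stated, but nothing on food between draws. With no aerosol effect and a session shift d (noncentral t, noncentrality d√n), p < 0.05 occurs in:
- n = 20: 7%, 25%, 56% for d = 0.1, 0.3, 0.5
- n = 30: 8%, 36%, 75%

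**5. Between metrics.** Suppose two metrics both truly change by 0.5 SD. Power p for each is 0.5645 (n = 20) or 0.7540 (n = 30). If they are independent, exactly one is significant with probability 2p(1 − p): 2 × 0.5645 × 0.4355 = 49%, and 2 × 0.7540 × 0.2460 = 37%. At correlation 0.56 the rates fall to about 31–32% and 25%. Separate tests can therefore split two metrics that respond equally.

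**The case against.** **The R-squared sentence is only an expectation, and mean change is tested elsewhere.** True: paired t-tests are planned for both qMRI and blood. But the sentence attaches the causal conclusion to R-squared and not to those tests.

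**The simulated rates are built in.** Largely true. Setting the population value at 0.81 and counting samples above 0.80 must give a high rate. That value is the plan's own expectation, and the point is the contrast with the paired test. The conclusion rests on the algebra.

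**Each subject is their own control.** Pairing removes stable differences between people. It does not remove effects of time or repeat testing.

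**Metric comparison is not limited to p-values.** Fair. Fractional changes put the metrics on a unit-free scale, a regression on changes is also planned, and nothing says metrics will be ranked by p-value. Still, fractional change is not scaled to each metric's variability, and no contrast between metrics is specified.

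**Stronger readings the text does not support.** A reader might infer that the missing no-aerosol session is what defeats the R-squared claim; on the marker-change reading it is not. A reader might infer that session drift could easily produce 80% on the pre/post reading; drift alone would have to be very large, so I claim no rate. Nor can one say that the trial has no control at all: the description refers to "the functional and mechanical metrics described in the previous section", which the supplied text lacks, and does not state the number of visits.

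**Conclusion.** The concern holds in limited form. On either plausible outcome, a joint R-squared above 80% does not show that aerosol promotes systemic EDF. On the marker-change reading this is exact for constant shifts in the analysed changes and needs no assumption about n or drift. Separately, as far as the supplied text goes, paired changes support a statement about before versus after a session that includes aerosol, not about aerosol alone. No planned analysis supports the most-sensitive claim.

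The rates above depend on assumed n, SDs, shifts and correlations. They show that the inferences can fail, not that they will. Session bias is possible, not demonstrated, and its direction is unknown. This should be fixed because it concerns the plan's main conclusions; the paired tests remain usable as descriptions of change.

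**What to change.** (a) **Analyses.** Delete the clause that begins with "indicating" and runs through the words systemic EDF. Name the regression outcome. Report R-squared as association across subjects or, if the outcome is pre versus post, as separation of the two time points. Base statements of change on the paired tests, worded as change from before to after a session that includes an aerosol challenge.

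(b) **Data and Statistical Analysis.** Replace the most-sensitive sentence with each metric's standardised pre-to-post change and 95% confidence interval. For scale, an observed standardised change of 0.5 has an interval of 0.03 to 0.96 at n = 20 and 0.12 to 0.88 at n = 30. Say that one metric changed more than another only from a paired within-subject contrast of standardised changes, for example a subject-level bootstrap interval for the difference. Call this responsiveness over the session, not sensitivity to aerosol.

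(c) **Limitation.** State that there is no comparison without aerosol, by endpoint: repeat cuff and breath-hold testing and the puffing manoeuvre for qMRI; time of day and fed state for the six-hour draw.

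The mismatch between the title, the nicotine wording in the analysis section and the nicotine-free challenge in non-smokers is a separate point that the sponsor needs to reconcile.

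The cost is wording, plus intervals and a contrast computed from data already planned. The conclusion becomes less favourable and non-causal. No extra visit, scan or blood draw is needed.
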